6.3.3. Activity

1. Participants will abstain from strenuous exercise for 24 hours before each blood collection for clinical laboratory tests. Participants may participate in light recreational activities during studies (e.g., watching television, reading).

6.4. Screen Failures

Screen failures are defined as participants who consent to participate in the clinical study but are not subsequently entered into the study. A minimal set of screen failure information is required to ensure transparent reporting of screen failure participants to meet the Consolidated Standards of Reporting Trials (CONSORT) publishing requirements and to respond to queries from regulatory authorities. Minimal information includes demography, screen failure details, eligibility criteria, and any serious adverse event (SAE).

Individuals who do not meet the criteria for participation in this study (screen failure) may not be rescreened.

7. Treatments

Study treatment is defined as any investigational treatment(s), marketed product(s), placebo, or medical device(s) intended to be administered to a study participant according to the study protocol.

7.1. Treatments Administered

Study Treatment Name:	ANA001	Placebo
Dosage formulation:	Size 0 capsule	Size 0 capsule
Unit dose strength(s)/ Dosage level(s):	250 mg/capsule	NA
Route of Administration	oral	oral
Dosing instructions:	4, 6, 8, or 12 capsules with light meal or snack ^a	4, 6, 8, or 12 capsules with light meal or snack ^a
Packaging and Labeling	Bulk bottle	
Storage conditions	Capsules (ANA001 or matching placebo) should be stored at controlled room temperature (20-25 °C) out of direct sunlight.	
Manufacturer	ANA Therapeutics, Inc.	

^a 500 to 750 cal

7.2. Dose Modification

The dose(s) and schedule (BID or TID) in the MAD part will be determined following review of the safety and PK data from the SAD part. Total daily doses will not exceed 2000 mg.

7.3. Method of Treatment Assignment

Within each cohort, participants will be randomly assigned to active drug or placebo as they qualify for the study using a computer-generated randomization.

7.4. Blinding

Participants will be randomly assigned to receive study treatment. Investigators will remain blinded to each participant's assigned study treatment throughout the course of the study. In order to maintain this blind, an otherwise uninvolved 3rd party (e.g., site pharmacist) will be responsible for the dispensation of all study treatment and will endeavor to ensure that there are no differences in time taken to dispense following randomization.

7.5. Preparation/Handling/Storage/Accountability

The Investigator or designee must confirm appropriate temperature conditions have been maintained during transit for all study treatment received and any discrepancies are reported and resolved before use of the study treatment.

Only participants enrolled in the study may receive study treatment and only authorized site staff may supply or administer study treatment. All study treatments must be stored in a secure, environmentally controlled, and monitored (manual or automated) area in accordance with the labeled storage conditions with access limited to the Investigator and authorized site staff.

The Investigator, institution, or the head of the medical institution (where applicable) is responsible for study treatment accountability, reconciliation, and record maintenance (i.e., receipt, reconciliation, and final disposition records).

7.6. Treatment Compliance

Participants will receive study treatment under the direct supervision of the Investigator or designee. A hand- and mouth check will be done to ensure that the participants swallowed the drugs.

7.7. Concomitant Therapy

Any medication or vaccine (including over-the-counter or prescription medicines, vitamins, and/or herbal supplements) that the participant is receiving at the time of enrollment or receives during the study must be recorded along with:

- Reason for use
- Dates of administration including start and end dates
- Dosage information including dose and frequency

The Medical Monitor should be contacted if there are any questions regarding concomitant or prior therapy.

Participants must abstain from taking prescription or nonprescription drugs (including vitamins and dietary or herbal supplements) within 7 days (or 14 days if the drug is a potential enzyme inducer) or 5 half-lives (whichever is longer) before the start of study treatment until completion of the follow-up visit, unless, in the opinion of the Investigator and Sponsor, the medication will not interfere with the study.

Acetaminophen, at doses of \leq 2 grams/day, is permitted for use any time during the study. Other concomitant medication may be considered on a case-by-case basis by the Investigator.

7.7.1. Rescue Medicine

No rescue medication will be provided.

7.8. Treatment after the End of the Study

Participants will not receive study drug (ANA001 or matching placebo) after the end of the study.

8. Discontinuation/Withdrawal Criteria

8.1. Discontinuation of Study Treatment

An unexpected AE related to study drug could lead to temporary or permanent discontinuation of a participant's study treatment, as determined by the Medical Monitor or Investigator.

8.2. Withdrawal from the Study

A participant may withdraw from the study at any time at his/her own request, or may be withdrawn at any time at the discretion of the Investigator for safety, behavioral, compliance, or administrative reasons.

If the participant withdraws consent for disclosure of future information, the Sponsor may retain and continue to use any data collected before such a withdrawal of consent.

If a participant withdraws from the study, he/she may request destruction of any samples taken and not tested, and the Investigator must document this in the site study records.

See SoA ([Section 2](#)) for data to be collected at the time of study discontinuation and follow-up and for any further evaluations that need to be completed.

Participants who withdraw will not be replaced.

8.3. Lost to Follow Up

A participant will be considered lost to follow-up if he or she repeatedly fails to return for scheduled visits and is unable to be contacted by the study site.

The following actions must be taken if a participant fails to return to the clinic for a required study visit:

- The site must attempt to contact the participant and reschedule the missed visit as soon as possible and counsel the participant on the importance of maintaining the assigned visit schedule and ascertain whether or not the participant wishes to and/or should continue in the study.
- Before a participant is deemed lost to follow up, the Investigator or designee must make every effort to regain contact with the participant (where possible, 3 telephone calls and, if necessary, a certified letter to the participant's last known mailing address or local equivalent methods). These contact attempts should be documented in the participant's medical record.
- Should the participant continue to be unreachable, he/she will be considered to have withdrawn from the study with a primary reason of lost to follow-up.

9. Study Assessments and Procedures

- Study procedures and their timing are summarized in the SoA. Protocol waivers or exemptions are not allowed.
- Immediate safety concerns should be discussed with the Sponsor immediately upon occurrence or awareness to determine if the participant should continue or discontinue study treatment.
- Adherence to the study design requirements, including those specified in the SoA, is essential and required for study conduct.
- All screening evaluations must be completed and reviewed to confirm that potential participants meet all eligibility criteria. The Investigator will maintain a screening log to record details of all participants screened and to confirm eligibility or record reasons for screening failure, as applicable.
- Procedures conducted as part of the participant's routine clinical management (e.g., blood count) and obtained before signing of the ICF may be utilized for screening or baseline purposes provided the procedures met the protocol-specified criteria and were performed within the time frame defined in the SoA.

Volume of Blood to be Collected From Each Subject - SAD

Type of Sample	Volume per Sample (mL)	No. of Samples/ Subject	Total Volume of Blood (mL) ^a
Safety (including screening and post treatment assessments)			
- Hematology	4	4	16
- Serum chemistry	8.5	4	34
serology (HIV, hepatitis)	8.5	1	8.5
serum β-hCG pregnancy test	3	1	3
Pharmacokinetic samples - SAD	4	10	40
Total – SAD			101.5

^a Calculated as number of samples multiplied by amount of blood per sample.

Volume of Blood to be Collected From Each Subject - MAD

Type of Sample	Volume per Sample (mL)	No. of Samples/ Subject	Total Volume of Blood (mL) ^a
Safety (including screening and post treatment assessments)			
- Hematology	4	6	64
- Serum chemistry	8.5	6	51
serology (HIV, hepatitis)	8.5	1	8.5
serum β-hCG pregnancy test	3	1	3
Pharmacokinetic samples – MAD (BID/TID)	4	25/28	100/112
Total – BID			226.5
Total - TID			238.5

^a Calculated as number of samples multiplied by amount of blood per sample.

Approximately 102 mL of blood will be collected during the SAD part. During the MAD, approximately 227 mL will be collected following BID dosing and 239 mL during TID dosing.

9.1. Safety Assessments

Safety assessments include incidence and frequency of AEs/SAEs, study drug discontinuation due to an AE (MAD portion only), use of concomitant medications, and changes from baseline in clinical laboratory tests, vital signs, electrocardiograms (ECG), and physical examinations.

9.1.1. Physical Examinations

A complete physical examination, conducted at screening, will include, at a minimum, assessments of the Skin, Cardiovascular, Respiratory, Gastrointestinal, and Neurological systems. Height and weight will also be measured and recorded.

A brief physical examination will include, at a minimum, assessments of the Cardiovascular, Respiratory, Gastrointestinal systems.

9.1.2. Vital Signs

Vital signs should be taken in a quiet setting without distractions (e.g., television, cell phones) and before any blood collections.

Oral temperature, pulse rate, respiratory rate, and blood pressure will be assessed.

Blood pressure and pulse measurements will be assessed with a completely automated device after 3 to 5 minutes rest in a supine position. Manual techniques will be used only if an automated device is not available.

Blood pressure and pulse measurements will be measured after 3 to 5 minutes rest in a supine position.

9.1.3. Electrocardiograms

A single ECG will be obtained for screening and at 3 hours after dosing during the SAD portion of the study and at Screening and 3 hours after dosing on Day 7 during the MAD portion. An ECG machine that automatically calculates the heart rate and measures PR, QRS, QT, and QTc intervals will be used.

9.1.4. Clinical Safety Laboratory Assessments

See [Appendix 2](#) for the list of clinical laboratory tests to be performed and the SoA ([Section 2](#)) for the timing and frequency.

The Investigator must review the laboratory report, document this review, and record any clinically relevant changes (as per the reference laboratory values [[Appendix 6](#)]) occurring during the study in the AE section of the CRF. The laboratory reports must be filed with the source documents. Clinically significant abnormal laboratory findings are those which are not associated with the underlying disease, unless judged by the Investigator to be more severe than expected for the participant's condition.

All laboratory tests with values considered clinically significantly abnormal during participation in the study should be repeated until the values return to normal or baseline or are no longer considered clinically significant as per the reference laboratory values in [Appendix 6](#).

- If such values do not return to normal/baseline within a period of time judged reasonable by the Investigator, the etiology should be identified and the Sponsor notified.
- All protocol-required laboratory assessments, as defined in Appendix 2, must be conducted in accordance with the laboratory manual and the SoA.
- If laboratory values from non-protocol specified laboratory assessments performed at the institution's local laboratory require a change in participant management or are considered clinically significant as given in [Appendix 6](#) (e.g., SAE or AE or dose modification), then the results must be recorded in the CRF.

9.2. Adverse Events

The definitions of an AE or SAE can be found in [Appendix 4](#).

AE will be reported by the participant (or, when appropriate, by a caregiver, surrogate, or the participant's legally authorized representative).

The Investigator and any designees are responsible for detecting, documenting, and recording events that meet the definition of an AE or SAE and remain responsible for following up AEs that are serious, considered related to the study treatment or study procedures, or that caused the participant to discontinue the study.

9.2.1. Time Period and Frequency for Collecting AE and SAE Information

All AEs and SAEs will be collected from the signing of the ICF until the follow-up visit at the time points specified in the SoA ([Section 2](#)).

Medical occurrences that begin before the start of study treatment but after obtaining informed consent will be recorded on the Medical History/Current Medical Conditions section of the case report form (CRF) not the AE section.

All SAEs will be recorded and reported to the Sponsor or designee within 24 hours, as indicated in Appendix 4. The Investigator will submit any updated SAE data to the Sponsor within 24 hours of it being available.

Investigators are not obligated to actively seek AEs or SAEs in former study participants. However, if the Investigator learns of any SAE, including a death, at any time after a participant has been discharged from the study, and he/she considers the event to be reasonably related to the study treatment or study participation, the Investigator must promptly notify the Sponsor.

The method of recording, evaluating, and assessing causality of AEs and SAEs and the procedures for completing and transmitting SAE reports are provided in Appendix 4.

9.2.2. Method of Detecting AEs and SAEs

Care will be taken not to introduce bias when detecting AEs and/or SAEs. Open-ended and non-leading verbal questioning of the participant is the preferred method to inquire about AE occurrences.

9.2.3. Follow-up of AEs and SAEs

After the initial AE/SAE report, the Investigator is required to proactively follow each participant at subsequent visits/contacts. All SAEs will be followed until resolution, stabilization, the event is otherwise explained, or the participant is lost to follow-up (as defined in [Section 8.3](#)). Further information on follow-up procedures is given in [Appendix 4](#).

9.2.4. Regulatory Reporting Requirements for SAEs

Prompt notification by the Investigator to the Sponsor of an SAE is essential so that legal obligations and ethical responsibilities towards the safety of participants and the safety of a study treatment under clinical investigation are met.

The Sponsor has a legal responsibility to notify both the local regulatory authority and other regulatory agencies about the safety of a study treatment under clinical investigation. The Sponsor will comply with country-specific regulatory requirements relating to safety reporting to the regulatory authority, Institutional Review Boards (IRB)/Independent Ethics Committees (IEC), and Investigators.

Investigator safety reports must be prepared for suspected unexpected serious adverse reactions (SUSAR) according to local regulatory requirements and Sponsor policy and forwarded to Investigators as necessary.

An Investigator who receives an Investigator safety report describing a SAE or other specific safety information (e.g., summary or listing of SAEs) from the Sponsor will review and then file it along with the Investigator's Brochure and will notify the IRB/IEC, if appropriate according to local requirements.

9.2.5. Pregnancy

Details of all pregnancies in female participants and, if indicated, female partners of male participants will be collected after the start of study treatment and until 30 days after the last dose.

If a pregnancy is reported, the Investigator should inform the Sponsor within 24 hours of learning of the pregnancy and should follow the procedures outlined in [Appendix 5](#).

Abnormal pregnancy outcomes (e.g., spontaneous abortion, fetal death, stillbirth, congenital anomalies, ectopic pregnancy) are considered SAEs.

9.3. Stopping Rules in Response to SAEs or Other Events

Dose-limiting toxicity AEs will be defined as Grade ≥ 3 , treatment-emergent, treatment-related laboratory abnormalities (Appendix 6) or AEs per the grading system by [US Department of Health and Human Services](#) (CTCAE, Version 5.0)The following Stopping Criteria will be used:

Clinical Findings:

1. Anaphylaxis or Grade ≥ 3 skin rash or pruritis
2. Grade ≥ 3 nausea, emesis or diarrhea

Laboratory Findings:

1. Evidence of new onset of acute renal or hepatic failure, defined by increases in BUN, creatinine, or LFTs (AST, ALT, Alkaline phosphatase) that reflect new evidence of Grade 3 thresholds for liver function tests, for creatinine, and for electrolytes attributable to the administration of drug in the context of the Investigator's evaluation.
2. Evidence of acute infection or inflammation, defined by changes in the WBC and differential, attributable to the administration of drug in the context of the Investigator's evaluation.
3. Any "unexpected" Grade ≥ 3 laboratory test result.

If one of the above clinical or laboratory criteria for stopping occurs in any subject, further study recruitment and subject dosing will be halted until a full safety assessment can be completed. Unblinding of the affected subject will be performed and the PI and Sponsor will review the totality of clinical data and any other circumstances possibly related to the "Stopping Criteria" findings to determine if the study can be resumed, modified, or will be permanently terminated.

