Sponsor	ANA Therapeutics, Inc. [name]
Principal Investigator	[name] WCCT Global [name]
Medical Monitor	[name] [name]
Biostatistics and Pharmacokinetics	[name] Inference, Inc. [name]
Clinical laboratory	Innovative Bioanalysis, LLC [name]
Bioanalytical laboratory (PK-analysis)	Medpace Bioanalytical Laboratories [name] [contact] [contact]

Protocol Amendment History

Date	Description
24-Dec-20	
Amendment 1
 
The protocol is amended to address comments received by the FDA as follows:
 
- Revising the Inclusion criteria pulse rate limits from 40 -100 bpm to 50 – 100 bpm- Providing reference laboratory values that will be used to determine if laboratory results are considered clinically significant- Providing a standard toxicity grading scale- Providing of detailed individual and dose level stopping criteria based upon the known safety profile and mechanism of action of ANA001 (niclosamide)- Limiting the total daily dose in the MAD portion of the protocol to 2000 mg
	
Page 8. MAD
 
Total daily doses are anticipated to range between will not exceed 2000 mg and 4500 mg of ANA001.

	
Page 18. Section 3.3 Benefit/Risk Assessment
 
The current SAD/MAD study is designed to explore the safety and PK of dosing greater than up to 2000-3000 mg/day as a single dose and regimens not to exceed 2000 mg/day as divided doses BID or TID.

	
Page 20. MAD
 
Total daily doses are anticipated to range between will not exceed 2000 mg and 4500 mg of ANA001.

	
Page 21. Section 5.5 Justification for Dose
 
The current study is designed to assess the safety of single doses of ANA001 exceeding up to 3000 2,000 mg and multiple dosing regimens up to not to exceed 2000 mg daily divided either BID or TID.

Date	Description

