3.2.3. Safety

Between 1971 and 1978, niclosamide was administered to 6365 patients under a US IND. Doses were up to and including 2000 mg/day for 7 days. There were 2385 evaluable patients, of which 13.3% reported side effects, all of which were mild or moderate, with none requiring treatment discontinuation. These included nausea/emesis in 4.1%, abdominal discomfort/loss of appetite in 3.4%, diarrhea in 1.6%, drowsiness/dizziness/headache in 1.4%, and skin rash/pruritis in 0.3% of patients (NDA 018669 Review Documentation).

In addition, according to the Safety Review of Niclosamide, Pyrantel, Triclabendazole and Oxamniquine report of the World Health Organization (WHO), there have been 84 reported adverse drug reactions related to niclosamide between 1975 and 2004 in the WHO database. They include 173 reports from 16 countries and the most common reactions are related to skin and appendages (41 reports), gastrointestinal tract (37 reports), cardiovascular system (28 reports) and anaphylactic reactions (9 reports).

Niclosamide was approved as a pregnancy class B drug and is thus safe to use during pregnancy.

Summarized below are safety assessment findings reported in the available literature:

- Prostate cancer patients received 500 mg and 1000 mg of niclosamide orally thrice per day for 15 days. TID regimens of >500 mg PO per day suggested the potential for DLT, however these findings are confounded by coadministration of antineoplastic treatment associated with a similar range of GI disturbances and occurred after niclosamide was dosed for >7 days ([Schweizer et al., 2018](#)).
- Colorectal cancer patients received 2000 mg of niclosamide orally once per day until disease progression or toxicity (up to four months). No adverse side effects were reported ([Burock et al., 2020](#)).

- 2000 mg niclosamide/person did not result in hematological changes ([Andrews et al., 1982](#)).
- No induction of methemoglobinemia was observed in men after oral administration of 30 mg/kg b.w. (~2000 mg/person) ([Andrews et al., 1982](#)).
- Men and women received 1000 mg niclosamide once or twice per person; children (6-15 years of age) received 750-1000 mg/person; neither scenario resulted in signs of intoxication ([Andrews et al., 1982](#)).

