3.3. Benefit/Risk Assessment

Niclosamide is approved for dosing up to 2000 mg PO daily for 7 days. There is limited safety and PK data in humans receiving more than 2000 mg as a single dose and/or more frequently than once daily. The current SAD/MAD study is designed to explore the safety and PK of dosing up to 3000 mg/day as a single dose and regimens not to exceed 2000 mg/day as divided doses BID or TID. In light of the immediate pressing need for development of an effective and safe oral therapeutic that can prevent progression of COVID-19, the benefit to risk ratio for the study is anticipated to be justified.

More detailed information about the known and expected benefits and risks and reasonably expected adverse events of ANA001 may be found in the Investigator's Brochure.

4. Objectives and Endpoints

Objectives	Endpoints
Primary	
• To assess safety and tolerability of single oral daily doses of ANA001 (1000 mg, 2000 mg and 3000 mg)• To assess safety and tolerability of multiple daily oral doses (twice daily [BID] or thrice daily [TID]) of ANA001 for 7 days
Secondary	
• Incidence of adverse events (AEs), serious AEs (SAEs), study drug discontinuation due to an AE (MAD portion only), use of concomitant medications, and change from baseline in clinical laboratory tests, vital signs, electrocardiograms (ECG), and physical examinations
	
• To assess the PK of single and multiple doses of ANA001• AUC_{0-t}, AUC_{0-last}, $AUC_{0-\infty}$ (SAD only), C_{max}, t_{max}, $t_{1/2}$, CL/F, V_z/F

5. Study Design

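### The mandatory halt in Protocol 9.3 covers five listed criteria only, so a related Grade 3 or higher clinical event or related SAE off the list, or a death, triggers no pre-specified halt

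*Protocol*

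**What the plan says.** Protocol 9.3 has three components.

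- **A definition.** "Dose-limiting toxicity AEs will be defined as Grade" 3 or higher, treatment-emergent and treatment-related. It covers both laboratory abnormalities and AEs, graded by CTCAE version 5.0.
- **A list of stopping criteria.** The two clinical items are (1) anaphylaxis, or rash or pruritus of Grade 3 or higher, and (2) nausea, emesis or diarrhea of Grade 3 or higher. The three laboratory items are (1) new renal or hepatic failure at Grade 3 thresholds attributed to drug, (2) infection or inflammation on the white-cell indices attributed to drug, and (3) any Grade 3 or higher laboratory result that is unexpected.
- **A consequence.** "If one of the above clinical or laboratory criteria for stopping occurs in any subject, further study recruitment and subject dosing will be halted" pending a safety assessment. "Unblinding of the affected subject will be performed", and the principal investigator and sponsor then decide whether to resume, modify or terminate.

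The Amendment 1 entry in the Protocol Amendment History says the criteria were added after FDA comments and rest on the drug's known safety profile and mechanism. Section 3.2.3 describes that profile. In an earlier IND series, 13.3% of 2385 evaluable patients reported side effects, "all of which were mild or moderate, with none requiring treatment discontinuation". They are itemised as "nausea/emesis in 4.1%, abdominal discomfort/loss of appetite in 3.4%, diarrhea in 1.6%, drowsiness/dizziness/headache in 1.4%, and skin rash/pruritis in 0.3% of patients".

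Section 3.3 states: "There is limited safety and PK data in humans receiving more than 2000 mg as a single dose". The same sentence extends the caveat to dosing more often than once a day. Under Section 7.2 the MAD doses and schedule "will be determined following review of the safety and PK data from the SAD part".

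**The concern.** The definition of dose-limiting toxicity is broad and the list that triggers action is narrow. Nothing connects the two. The heading of 9.3 refers to SAEs, yet neither an SAE nor a death is a criterion. Staff who follow the text exactly could dose the next participant, or open the next cohort, after an event that the same section calls dose-limiting. Whether to pause would then be decided ad hoc.

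This matters because the participants are healthy volunteers, the capsule is in its first clinical use, cohort S3 receives 3000 mg, and MAD divides the dose BID or TID. By the protocol's own account, the last two are areas with limited data. What is at stake is participant safety.

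**Working it through.** There is no plan figure to reproduce: the documents give no operating characteristics for the stopping rule. The check is a reading of the text, followed by a rough sizing.

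**Step 1. What triggers the halt.** 2 clinical + 3 laboratory = 5 criteria. None names an SAE, a death, or related Grade 3 or higher clinical AEs in general. The only catch-all covers laboratory results. No criterion uses ECG or vital signs, although both are collected. The defined term is given no action in 9.3, elsewhere in the protocol, or in the SAP.

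**Step 2. Whether another provision requires a study-level halt.**

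- Protocol 5.4: sequential cohorts make early stopping possible; no event, threshold or action is given.
- Protocol 8.1, 8.2 and the opening of Section 9: one participant's treatment or participation.
- Protocol 9.2.1 and 9.2.4: SAE reporting within 24 hours and regulatory notification; no halt.
- Protocol 7.2 and 10.3.3, SAP 1.2 and 1.3: a data review after S1 to S3, used to set MAD dosing or a possible fourth SAD cohort. No review is specified before S2, before S3, or between M1, M2 and M3.
- Appendix 3: the sponsor may terminate at its sole discretion; IRB notification and immediate-hazard changes are provided for.

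None of these is a mandatory halt. Within each part, 9.3 is the only one.

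**Step 3. Test events.**

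- Fatal anaphylaxis, or drug-related hepatic failure at Grade 3 thresholds: the halt applies, through a listed criterion.
- Related Grade 3 arrhythmia, syncope or seizure without anaphylaxis or a qualifying laboratory change: dose-limiting by definition, no halt.
- Related SAE of a type not listed: reported within 24 hours, no halt.
- Death without a listed finding: no halt.

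Two of the five side-effect groups in 3.2.3 are also off the list at any grade: abdominal discomfort/loss of appetite, and drowsiness/dizziness/headache. The WHO reports cited there include 28 cardiovascular and 9 anaphylactic. Anaphylaxis is listed; no cardiovascular event is.

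**Step 4. Rough frequency, S1 and S2 only.** Input from 3.2.3: 0 severe side effects in 2385 evaluable patients at up to 2000 mg/day for 7 days. Severe is taken to correspond to Grade 3 or higher (assumption).

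- One-sided 95% upper bound: 1 − 0.05^(1/2385) = 0.001255, or 0.13%.
- Active participants in S1 and S2: 8 + 8 = 16.
- Chance of at least one event at that bound: 1 − (1 − 0.001255)^16 = 0.0199, or 2.0%.

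This counts severe events of every kind, including those already listed, so it overstates the off-list part. It also rests on an earlier formulation and on 2385 evaluable of 6365 treated patients. It is not carried to S3 (above 2000 mg) or to MAD (more often than once daily), because 3.3 describes the data as limited for both.

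**The case against.** **Intent.** The definition leads straight into the list under a heading that mentions SAEs, so the sponsor may have meant every dose-limiting event to count. That is plausible. But the definition precedes the sentence introducing the criteria, and the halt refers to the clinical or laboratory criteria for stopping. If every related Grade 3 or higher event already counted, listing nausea, emesis and diarrhea at that grade would add little. At best the text is ambiguous, and clarifying it takes the same edit.

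**Other safeguards.** Safety concerns go to the sponsor at once, SAEs within 24 hours, and the IRB and regulators are informed. The list followed FDA comments and covers the nausea/emesis, diarrhea and rash/pruritus groups. This stands, and it narrows the practical risk. It does not supply a mandatory pause.

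**Stronger readings that the documents do not support.**

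- A reader might infer that the trial cannot be stopped after such an event. It can: 5.4 and Appendix 3 leave the sponsor free to act.
- A reader might infer that nobody reviews safety before MAD. Section 7.2 and SAP 1.3 provide for that review.
- A reader might size the gap from the side-effect groups left off the list. All reported effects were mild or moderate, so those percentages say nothing about Grade 3 or higher events.
- A reader might extend the 0.13% bound to S3 or MAD. Besides 3.3, Section 3.2.3 mentions possible dose-limiting toxicity with TID dosing in prostate cancer patients. That signal is confounded by co-treatment and arose after more than 7 days, but it is enough to bar claiming a low rate.

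**Conclusion.** The point holds as a missing pre-specified halt within SAD and within MAD. Followed literally, the rule lets dosing continue after a related Grade 3 or higher clinical event off the list, a related SAE off the list, or a death, unless a listed criterion is also met or someone chooses to stop.

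Its size is structural: none of the five criteria reaches these events as a class. On frequency, the 2.0% for S1 and S2 is a rough guide that assumes the earlier series transfers to the new capsule. For S3 and for BID/TID dosing no rate is claimed in either direction. The change should be made because it is cheap and the consequence of an omitted pause could be serious.

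**What to change.** Add two lines to the Clinical Findings list in Protocol 9.3:

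- *3. Any other Grade 3 or higher (CTCAE v5.0) treatment-emergent clinical AE considered related to study drug.*
- *4. Any SAE considered related to study drug, and any death.*

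Line 3 is confined to clinical AEs on purpose. Importing the whole dose-limiting definition would make every related Grade 3 or higher laboratory result a trigger and override the restriction to unexpected results in laboratory criterion 3. Death carries no relatedness condition because attribution is a question for the review that follows the pause. Leave the laboratory criteria and the halt, unblinding and review paragraph as they are. Record a CTCAE grade for each AE beside the Appendix 4 intensity, which is now only mild, moderate or severe; the existing criteria already depend on that grade.

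**Cost.** No new visits, procedures or participants; one grade per AE; an occasional pause.

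- In SAD each participant has a single dose, so a pause delays only those not yet dosed.
- In a MAD cohort of 12, a pause during Days 1 to 7 could interrupt up to 11 others. That could compromise Day 7 PK and the Day 7/Day 1 ratios for 9 of the 27 MAD actives (3 × 9), and Section 8.2 does not replace withdrawals. The power model in SAP 7.3 is optional, so no committed analysis is lost there.
- Each halt unblinds one participant. For reviewers who know the allocation ratio, the chance that another cohort member is on active moves from 8/10 = 80% to 7/9 = 78% or 8/9 = 89% in SAD. In MAD at 9:3 it moves from 9/12 = 75% to 8/11 = 73% or 9/11 = 82%.

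These costs are acceptable for a temporary pause after an event of this seriousness in healthy volunteers.
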